**COMPENSATION FOR RESEARCH-RELATED INJURY**

The use of a suture for closure of deep internal tissues is within the standard of care, and there are risks of infection, need for repeat surgery, wounds, and delayed infection as there are with any surgical suture. It is not thought that closure with a Mesh Suture will significantly change those risks. Therefore, there will be no compensation for research related injury. However, in the case of postoperative complications related to the Mesh Suture within the course of the study (1 year after the surgery with Mesh Suture), [name] will perform the revision surgery free of charge.

**ADDED ECONOMIC BURDEN TO PARTICIPANTS**

None. There are costs of surgery and postoperative follow-up that are unchanged with either using or not using the Mesh Suture.

**CONSENT PROCESS**

The consent will be obtained by the attending surgeon, or by the study coordinator. This will occur preferably in the clinical office of the attending, but also in the preoperative holding area before surgery. We expect the consent process to take 10 minutes. Suture examples will be shown to the

patient. Steps taken to minimize coercion or influence will be contained in the consent form. Consent will be obtained by native Armenian speakers.

All patients who meet inclusion criteria and who do not have exclusion criteria will be approached for consent, so long as their legal guardian or legal representative is present and consents to the orthopedic procedure.

#### **PROCESS TO DOCUMENT CONSENT IN WRITING**

The process to document consent and re-consent in writing will be done as follows, per GCP guidelines: the consent form will be signed and personally dated by the participant and/or the legal representative/guardian and by the person who conducted the consent prior to any study procedures. A signed copy of the consent form will be given to the participant or the legal representative. This process will be documented in the subject source documents.

#### **DRUGS OR DEVICES**

Three different sizes of Mesh Suture, namely 2-0, 0 and Number 2, will be under the control of the study coordinator, and will be disbursed in the operating room at the time of the procedure. The study coordinator will fill out the necessary patient data form at that time. For traceability, lot number and expiration date for finished and packaged suture will be recorded. The sutures will be locked in a cabinet in the operating room with keys controlled by Drs. [name] and [name]. They are labelled "For investigational use only".

### **The Wigmore Clinic**

Wigmore Clinic is a modern medical center, which offers wide range of inpatient and outpatient services in orthopedics, sport medicine, spine surgery, vascular surgery, pediatrics, dentistry and interventional radiology. The Clinic was founded in 2017. The clinic's facility is designed specifically to provide maximum comfortability and highest possible standards of care. Wigmore is a dynamic and rapidly growing medical center that has a commitment to evidence based clinical practice. Being affiliated with Yerevan State Medical University the clinic is involved in education and academic research. The clinic has a mission to build a culture of effective teamwork and quality: ensuring safe and patient focused care across all departments of the organization. Wigmore Clinic's values are: commitment to continual improvement, high moral and professional standards, trust, respect and transparency.

The advantage of Wigmore Clinic is the coordinated care in teams of experts, who are working to achieve the best results in treatment. Most of the leading surgeons of the hospital were trained in USA and Europe and created the wide network with medical specialists from these countries, who support the clinic in continual education and management of the most complicated cases.

## **Arabkir Medical Center**

“Arabkir” Joint Medical Center – Institute of Child and Adolescent Health (Arabkir JMC) is the largest pediatric hospital in Armenia, which realizes large-scale medical activities. The center provides medical services, including prevention, diagnostics and treatment of different child diseases, follow-up services for children with chronic urological and surgical, gastroenterological problems as well as with bronchial asthma, epilepsy, diabetes and hepatology, orthopedics, nephrology, endocrinology-related diseases, psycho-social and rehabilitation services.

“Arabkir” JMC also provides services for emergency cases and a number of services for adults in the fields of urology and general surgery, nephrology and kidney transplantation, laboratory diagnostics. As a multidisciplinary medical structure, Arabkir JMC provides medical assistance and care to thousands of children every year. The Service of Trauma and Orthopedics (STO) has a long history of providing high quality care to patients with musculoskeletal disorders. It is one of the leading departments not only in Armenia, but in the region. Many patients from neighbor countries such as Georgia, Russia, Ukraine, and Iran come to this Service for surgical treatment and rehabilitation. The hospital has several Child Development and Rehabilitation Centers function in different regions of Armenia.

## **TRACEABILITY**

Lot number, reference number, and date of expiration will be recorded for each case. In the event of need for follow-up of patients depending on information from the sponsor, it will be the responsibility of the PI to reach out and communicate with the patients in terms of need for follow-up, increased monitoring, and even surgery for addressing of the issue.

## **LIABILITY**

As is the custom for clinics and surgeons in Armenia, neither the Wigmore Clinic nor [name] carry malpractice insurance.

## **MISSING DATA**

It is the responsibility of the PI to accurately and completely fill out the CRF. Missing data will be analyzed by the data monitoring committee and completed with assistance of the PI. Follow-up either in person at the Wigmore Clinic or by telephone is the responsibility of the PI.

## **DATA FROM THE MEDICAL RECORD**

All patients in this study will grant approval for the appropriate aspects of their medical record (including the operative report, photographic documentation, x-rays, laboratory findings, culture reports, and other pertinent information to be included in the Clinical Evaluation Trial. Organizations

that may inspect and copy the medical chart include the IRB and other representatives of this institution, government agencies such as the US Food and Drug Administration (FDA) and other regulatory authorities in other countries including the European Union; and the study sponsor Mesh Suture Inc. The sponsor, monitors, auditors, the US Office for Human Research Protections (OHRP), the US FDA, as well as other government organizations may be granted direct access to the medical record to conduct and oversee the research.

## **DEVIATIONS FROM PROTOCOL**

Any deviation from the protocol judged minor will be documented by the PI and judged whether the patient and outcome will be included in the final report. Any deviation from the protocol judged major including will be communicated immediately with the data monitoring committee for resolution.

## **FINAL REPORT**

A final report of data will be provided by the PI to the sponsor. This will include an evaluation of all primary and secondary endpoints. Efforts will be made to obtain long term follow up either by office visits at the Wigmore Clinic, and/or telephonic interviews of subjects. Duramesh will be analyzed in terms of the size used, the location placed (tendon, joint capsule), running or interrupted closure, surgeon satisfaction, and a qualitative report of issues of use of the suture. The appropriate statistical tests including t-tests for the comparison of groups will be employed for data analysis.

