## **EXCLUSION CRITERIA**

1. No planned need for closure of deep soft tissues
2. Pregnancy
3. Age less than 1 year
4. Repair of skin or other tissues with epithelium

Indications for Use	The Mesh Suture is indicated for use in soft tissue approximation and/or ligation. Not to be used for the skin.
Patient Population	Subjects will be recruited from a population of patients treated for orthopedic conditions by [name]
Study Size and Center	N=80 patients at Wigmore Clinic Arabkir Joint Medical Center in Yerevan, Armenia
Clinical Study Design	Safety and efficacy trial of a medical device (surgical suture). Prospective, Non-blinded and non-randomized, Multi-center, Single-surgeon
Primary Safety Endpoints	Surgical site occurrence (SSO) with 30 postoperative days Delayed infection or sinus within 1-12 months
Secondary Effectiveness Endpoints	Operating room handling Rehospitalization for any wound issue within 30 days Return to the OR for any reason within 1-12 months General rating of the suture by surgeon
Study Flow	
SCREENING
 
 
1. Preoperative assessment by the surgeon to confirm that the patient meets the study entry criteria.
 
2. Informed consent obtained from patient by study staff.
 
 
SURGERY
 
 
1. Perform surgery and close deep tissues with Mesh Suture
 
2. Record intraoperative information on CRF.
 
 
PATIENTS EXCLUDED FROM FURTHER FOLLOW-UP
 
Based on the tissues, patient's condition, and all other intraoperative factors, [name] may decide not to use a mesh suture. These patients will not undergo any further follow-up nor be included in the safety and effectiveness analyses.
 
INITIAL FOLLOW-UP
 
Patient follow-up will be per [name] established protocols. All patients will be seen at least or contacted by study staff by 30 days to assess healing of the incision and assess for possible SSO.
 
FINAL FOLLOW-UP
 
Late patient follow-up will be per [name] established protocols. All patients will be seen at least or contacted by study staff by the end of the study period (12 months after the surgery) to assess healing of the incision, functional outcome of surgery, and assess for possible delayed infection.

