## **SAFETY AND EFFECTIVENESS**

This safety and effectiveness study is intended to demonstrate that overall patient outcomes are no worse than or adversely different from the current surgical standard of care. In addition to overall patient outcomes, the study will also examine adverse outcomes related to the use of the suture.

An overarching issue is that the suture used in the procedure reflects only a small part of the total treatment of the patient – including what adverse occurrences are responsible for surgical morbidity and mortality. Robust evaluation of suture closures is best assessed in the setting of an animal study where the surgical wound can be opened and tested at the end of the follow-up period. This then allows the investigator to readily inspect the suture line and assess the abdominal suture closure for safety and effectiveness endpoints including suture pull-through. This is not possible in the treatment of humans. Therefore, safety is best noted by the achievement of standard wound healing rates and the absence of delayed infections in comparison to historical controls. Efficacy is best noted by the achievement of standard functional outcomes in comparison to historical controls.

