## **DESCRIPTION AND ANALYSIS OF ALL INCREASED RISKS TO THE RESEARCH SUBJECTS**

1. All of these subjects will be undergoing orthopedic surgery, and there are established baseline rates of SSO for these procedures. Each hospital will have its own rate of SSO based on the procedures performed and the population of that facility. While all procedures are associated with risks and SSO, it is not expected that there will be significant ADDED risk to the patient using a mesh suture for a deep internal closure. In fact, animal data implies that using a mesh suture will result in a stronger earlier repair.
2. Patients undergoing surgery have other risks of medical complications. It is NOT expected that there will be additive medical risks of closing with mesh suture.
3. Mesh suture is made of a material commonly used for sutures (polypropylene), without any added chemicals. It is treated with heat and pressure – two items that are also used commercially in the fabrication of hernia meshes. The mesh suture has passed all of the necessary FDA tests for biocompatibility and the absence of toxins.
4. The surgeon does not need to alter their technique in any way.
5. It is expected that a mesh suture closure will take the same amount of time as closures with standard sutures.
6. Mesh Suture meets all of the criteria as other sutures for strength and the quality of the needle attachment. It is physically larger than other sutures, but achieves a small knot with the collapsing of the filaments.
7. The protocol allows the use of this suture in a vulnerable population, namely children under the age of 18. Polypropylene sutures have been used extensively in vascular and heart surgery in children as well as in other soft tissue procedures with an excellent record for biocompatibility. Therefore, use of mesh suture in this age group does not represent a significant added risk.

Examples from the literature are below of using polypropylene sutures and meshes in children:

- a. Perez-Negueruela C, Carretero J, Mayol J, Caffarena JM. Surgical closure of multiple large apical ventricular septal defects: how we do it. *Cardiol Young*. 2017;27(3):588-591.

- b. Baradaran N, Wood CM, McCoy OO, Prasad MM, Stec AA. Laparoscopic intra-abdominal patent processus vaginalis ligation in pediatric urology practice. *J Pediatr Urol.* 2017;13(5):512.e1-512.e6.

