### **CLOSURE OF THE STUDY**

For this first-in-human use of mesh suture, 80 cases will be performed in this safety and effectiveness study. The hypothesis is that the mesh suture will be equivalent in performance to standard suture. The study will be closed upon accrual of 80 patients, final follow-up of these patients. An early moratorium of the study will occur with a 15% rate of SSO, or 3 early and unexpected dehiscences of deep tissue closure attributable to the suture as judged by the data monitoring committee. Early closure of the study will occur based on the judgement of the PI, the sponsor, and an early demonstration of equivalence to the results of standard suture as judged by a lack of early and late infections and appropriate postoperative surgical results demonstrating appropriate tissue approximation for internal load-bearing closures.

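### The aim is to show Mesh Suture no worse than, or equivalent to, standard suture, but the only inferential method the protocol names is a test of difference, which cannot support that aim

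*Protocol*

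**What the plan says.** Safety and Effectiveness states that the study is "intended to demonstrate that overall patient outcomes are no worse than or adversely different from the current surgical standard of care". Closure of the Study adds: "The hypothesis is that the mesh suture will be equivalent in performance to standard suture". The design row of the synopsis table reads "Prospective, Non-blinded and non-randomized, Multi-center, Single-surgeon". All analysed patients receive Mesh Suture, so the comparison has to be external, and Safety and Effectiveness says so: "safety is best noted by the achievement of standard wound healing rates and the absence of delayed infections in comparison to historical controls".

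The section on increased risks says that "there are established baseline rates of SSO for these procedures" but gives no figure. The sample size is stated without derivation: "For this first-in-human use of mesh suture, 80 cases will be performed in this safety and effectiveness study".

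The one sentence on inferential method is in Final Report: "The appropriate statistical tests including t-tests for the comparison of groups will be employed for data analysis". It follows a sentence on describing Duramesh use by suture size, location, closure type and surgeon satisfaction.

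Two other rules bear on the point. An SSO rate of 15% triggers a moratorium (data monitoring section and Closure of the Study). Closure of the Study also allows early closure on a judgement of equivalence that rests on a lack of infections and on suitable surgical results, with no numerical threshold.

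**The concern.** A t-test for comparing groups, or an exact or chi-square test in its place, asks whether the data contradict equality. Failure to reject equality is not evidence of equality; with few events in 80 patients it is the likely result even when a real excess exists. A claim of no worse than standard needs the opposite set-up: the data must rule out an excess larger than a stated amount. The problem is the direction of the hypothesis. That a t-test suits a yes/no outcome poorly is secondary, since changing the test would not cure it.

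At stake is the safety conclusion of a first-in-human study of a permanent implant: a clinically relevant excess of SSO could be reported as consistent with equivalence.

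**Working it through.** **Inputs.** From the protocol: n = 80; moratorium at 15%, which at full accrual is 12/80 = 15%. Assumed, because the protocol gives none: reference SSO rate p0 of 3%, 5%, 8% or 10%; two-sided alpha 0.05; reference treated as a fixed number. The protocol has no power or margin figure to reproduce.

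**Step 1: non-significant counts.** The exact two-sided p-value of x events is the sum of P(X = k | 80, p0) over all k no more probable than x. Example at p0 = 5% (4 events expected), x = 8: P(X ≥ 8) + P(X = 0) = 0.0466 + 0.0165 = 0.063, not significant. For x = 9, p = 0.018. So 8/80 = 10%, an observed doubling, still counts as not different from 5%; its Clopper-Pearson 95% CI is 4.4% to 18.8%.

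**Step 2: chance of a non-significant result** when the true rate is f × p0: the sum of C(80, x)(f·p0)^x(1 − f·p0)^(80−x) over the non-significant counts.

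| p0 | Non-significant counts | True 1.5-fold | True 2-fold |
|---|---|---|---|
| 3% | 0–5 | 85% | 65% |
| 5% | 1–8 | 85% | 59% |
| 8% | 2–11 | 75% | 36% |
| 10% | 3–13 | 69% | 25% |

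**Step 3: effect of the moratorium.** Count only non-significant results with fewer than 12 events. At 3%, 5% and 8% the non-significant range already ends at 11 or below, so nothing changes. At 10%, counts 12 and 13 drop out: 69% falls to 45% (1.5-fold) and 25% to 10% (2-fold). This applies the 15% rule at full accrual.

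**Step 4: sensitivity.** Requiring the upper tail alone to be at most 0.025 raises the figures to 93% and 80% at p0 = 3% and to 79% and 35% at 10%; at 5% they hardly move. If the reference is itself a sample of 80 historical patients (two-sample test of proportions, normal approximation), non-significance is 91% and 78% at p0 = 5%, and 84% and 58% at 10%.

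**Step 5: what 80 patients can show under a confidence-bound rule.** Let p0 = 5% with the true rate also 5%, and require the Clopper-Pearson 95% upper limit to lie below p0 plus margin.

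| Margin (points) | Largest count that passes | Its upper limit | Chance of passing |
|---|---|---|---|
| 5 | 2 | 8.7% (< 10%) | 23% |
| 7.5 | 4 | 12.3% (< 12.5%) | 63% |
| 10 | 5 | 14.0% (< 15%) | 79% |

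**The case against.** The strongest reply is that Final Report never assigns the t-test to the equivalence hypothesis. The preceding sentence is about size, location and closure type, there is no concurrent control arm, and t-tests could be meant for the 1-to-5 handling scores. The word including also leaves other tests open. This reading is plausible and may be right. It does not remove the mismatch: the stated hypothesis then has no matching inferential method in the protocol.

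A second reply is that interval methods, margins and decision rules usually belong in a statistical analysis plan, which is not at hand. That holds for the missing margin, which is not the finding. What stands is that the protocol fixes the hypothesis itself and names, as its only inferential method, a kind of test that cannot answer it.

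Two stronger readings are tempting and unsupported. A reader might infer that the sponsor will declare equivalence from a non-significant p-value. No section says so: Safety and Effectiveness speaks of reaching standard healing rates, and the early-closure clause is a judgement without a p-value rule. A reader might also infer that a doubling of SSO would usually be missed. Against a fixed rate that holds only at references of about 5% or below; at 8% to 10% a doubling would usually be detected. The moratorium further limits unflagged harm at a 10% reference, although it is a safety stop and not a test of equivalence.

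**Conclusion.** The point holds as a mismatch between aim and named method. Tests of difference cannot support the no-worse-than or equivalence aim, and if they concern only Duramesh subgroups they do not bear on it. A non-significant result could be read as equivalence. Under the assumptions above, a 1.5-fold excess goes undetected more often than not at every assumed reference from 3% to 10%; the single exception is the 10% reference once the moratorium is counted, at 45%. A doubling goes undetected more often than not only at 3% to 5%.

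All percentages rest on assumed reference rates and an assumed alpha, and they shift by several points with the exact-test convention. The mismatch itself depends on none of them. It should be corrected before the outcome data are reviewed.

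**What to change.** In Final Report:

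- State that tests of difference will not be used to support a claim of no worse than or equivalent to standard suture.
- Report each primary outcome as a proportion with its exact (Clopper-Pearson) 95% CI.
- Claim no worse than historical controls only if the upper limit lies below a reference rate plus margin, both fixed and justified before outcome data are reviewed. Otherwise report the estimate and CI with no equivalence claim.
- Keep comparisons by suture size, location and closure type descriptive.

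The wording is a few sentences and needs no new patients. The real cost is in choosing and justifying a reference rate and margin, which the protocol does not contain, and in a claim that becomes harder to make. As Step 5 shows, with a 5% reference a truly equal suture would meet a 5-point margin in only about 23% of trials and a 10-point margin in about 79%. If a margin that wide cannot be justified, the report should be limited to estimation.

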1. LITERATURE REVIEW OF PRE-CLINICAL TESTING

1.1. Pre-clinical Rat *In-Vivo* Hernia Model using Mesh Suture Prototype

1.1.1. Objective

Demonstrate in an established rat hernia model a novel mesh suture prototype would have decreased pull-through in comparison to standard suture.

1.1.2. Methods

Incisional hernias were produced in N=30 rats according to an established hernia model. The rat hernias were randomized to repair with either two 5-0 polypropylene sutures or two mid-weight polypropylene mesh sutures. Standardized photographs were taken prior to repair and 1 month after repair.

Edge-detection software was used to define the border of the hernia defect and calculate the defect area. Histology was performed on all mesh suture specimens, with in-growth graded according to the ASTM 4-point scale.

1.1.3. Results

Table 1: Results from Rat Study

Study Endpoint	Mesh Suture Prototype	Conventional Suture
Randomization Assignment, N	17	13
Pulled-Through, n (%)	0 / 34 (0)	17 / 26 (65)
Mean Area of Recurrent Defects Following Repair, mm 	178	267
Change in Defect Area, %	57.4% Reduction	10.1% Increase
ASTM 4-Point Scale	Excellent (ASTM3) fibro-collagenous in-growth in 13/17 specimens	Good (ASTM2) in-growth in 4/13 suture specimens

[figure not shown]

Figure 1: Rat hernia repair data

[figure not shown]

Figure 2: Rat hernia repair images

